The PASI provides quantitative assessment of psoriasis lesional burden based on the amount of body surface area involved and degree of severity of erythema, induration, and scale, weighted by body part.^{43,44} A qualified Investigator or designee who has been trained by the sponsor/designee, if necessary, will perform the PASI assessment ([Appendix H](#)). The site should make every attempt to have the same qualified Investigator or designee perform all PASI assessments on a given subject throughout the study as specified in [Appendix C](#).

Body Surface Area (BSA)

BSA affected by psoriasis will be measured. The subject's right or left hand will be selected as the measuring device. For purposes of clinical estimation, the total surface of the palm plus five digits will be assumed to be approximately equivalent to 1% of BSA.⁴⁵ Measurement of the total area of involvement by the Investigator or delegated site staff is

aided by imagining if scattered plaques were moved so that they were next to each other and then estimating the total area involved. BSA will be measured as specified in [Appendix C](#).

Physician's Global Assessment of Disease Activity (PhGA)

PhGA will be evaluated on a 0-100 mm horizontal visual analogue scale (VAS) with a question referring to both musculoskeletal and skin disease activity currently⁴⁶ ([Appendix I](#)). The PhGA is to be performed at the visits described in [Appendix C](#).

Patient Reported Outcomes (PROs)

The subject should complete these questionnaires before site personnel perform any clinical assessments and before any interaction with site personnel has occurred to avoid biasing the subject's responses. Subjects will be instructed to follow the instructions provided with each instrument and to provide the best possible response to each item. Site personnel shall not provide interpretation or assistance to subjects other than encouragement to complete the tasks. Subjects will complete the following questionnaires at the visits specified in [Appendix C](#).

Patient's Global Assessment of Disease Activity (PtGA)

PtGA will be evaluated on a 100 mm horizontal VAS with a question referring to both arthritis and psoriasis disease activity over the past week.⁴⁶ The VAS is anchored by the opposite adjectives of "excellent" and "poor."

Patient's Global Assessment of Arthritis

Patient's Global Assessment of Arthritis will be performed on a 100 mm horizontal VAS with a question referring to arthritis disease activity over the past week.⁴⁶ The VAS is anchored by the opposite adjectives of "excellent" and "poor."

Patient's Assessment of Pain

Patient's Assessment of Pain will be performed on a 100 mm horizontal VAS with a question referring to pain over the past week.⁴⁶ The VAS anchors are "no pain" and "pain as bad as it could be."

Psoriatic Arthritis Impact of Disease (PsAID)

PsAID is a validated patient self-reported tool to assess the impact of PsA on patient's life. Two versions of the questionnaire were developed by an European League Against Rheumatism (EULAR) initiative: one for clinical practice (PsAID-12) and one for clinical trials (PsAID-9). Both contain physical and psychological domains. The PsAID-9 version will be used in this study.⁴⁷

Health Assessment Questionnaire Disability Index (HAQ-DI)

The HAQ-DI is a standardized measure of physical function in arthritis. The HAQ-DI questionnaire contains 20 items divided into 8 domains that measure: dressing and grooming, arising, eating, walking, hygiene, reach, grip, and common daily activities.⁴⁸

Short Form 36 Health Survey (SF-36)

SF-36 is a generic measure to assess patients' general health and well-being (i.e., health related quality of life). The short version 2 (SF-36v2) consisting of 36 questions will be used.^{49,50}

Dermatology Life Quality Index (DLQI)

DLQI is a measure of subject's quality of life (QoL) related to skin disease. The DLQI questionnaire consists of 10 questions concerning subjects' perception of the impact of skin diseases on different aspects of their health related quality of life over the last week. The items of the DLQI encompass aspects such as symptoms and feelings, daily activities, leisure, work or school, personal relationships and the side effects of treatment.⁵¹

Self-Assessment Psoriasis Symptoms (SAPS) v.3.0

The subject will rate his/her psoriasis symptoms within the past 24 hours utilizing an 11-item questionnaire.⁵²

Musculoskeletal Ultrasound (US)

Investigators will at study start indicate if they want to participate in the optional US assessments or not. If they decide to participate, they should, if possible, perform an US evaluation for every subject they enroll at visits indicated in [Appendix C](#).

For the sites participating in the optional US assessment, high-end ultrasound equipment is recommended. The US must be performed by an expert sonographer (rheumatologist or radiologist) with verifiable training and/or certification in ultrasonography, and at least 3 years of regular US experience. Prior experience in multicenter ultrasound study(ies) is recommended, otherwise training will be provided. The Ultrasonographer must be independent of the clinical Investigator and should be blinded for subject characteristics and treatment arm; he/she should be the same person throughout the study, and a back-up with the same qualifications should be appointed.

The assessments and scoring will be locally performed. US should be performed the same day as the clinical examination, or the day before the visit if not possible, and prior to injecting study medication. The subjects undergoing US evaluation should not take NSAIDs for the last 48 hours prior to the US assessment. (See Section [5.2.3.2 Prohibited Therapy](#)).

The ultrasound evaluation will comprise a comprehensive assessment of joints, entheses and tendons.

For the joint evaluation, the following 23 pairs of joints will be scanned:

- Metacarpophalangeal (MCP) joints 1 to 5,
- Proximal interphalangeal (PIP) joints 1 to 5,
- Distal interphalangeal (DIP) joints 2 to 5,

- Metatarsophalangeal (MTP) joints 1 to 5,
- Wrist, elbow, knee, ankle (tibiotalar).

The US assessment of synovitis will consist of an evaluation of hypoechoic synovial hyperplasia (SH) using Grayscale (or B mode) and synovial vascularization using Power Doppler (PDUS). The pre-specified set of 23 paired joints will be scanned in longitudinal and transverse scan from the dorsal aspect with the joint in a neutral position, except for the knee, which will also be examined in a flexed position (30°).

The presence of synovitis (i.e., SH and Power Doppler) will be scored according to the OMERACT-EULAR PDUS composite semi-quantitative scale (0 to 3).⁵³

For the entheses evaluation, the following 5 pairs of entheses will be scanned:

1. Common extensor tendon insertion at the lateral humeral epicondyle,
2. Quadriceps tendon insertion at the superior pole of the patella,
3. Patellar tendon proximal insertion at the inferior pole of the patella,
4. Patellar tendon distal insertion at the tibia tuberosity,
5. Achilles tendon insertion at the calcaneus; plantar aponeuroses insertion at the calcaneus.

Each evaluated enthesis will be scored in terms of inflammatory (i.e., presence of Doppler signal within 2 mm from the cortical bony insertion and hypoechogenicity of the tendon insertion with or without increase of its thickness) and structural lesions (i.e., cortical abnormalities erosions and enthesophytes, and calcifications) according to the OMERACT enthesitis composite semi quantitative scale (0 to 3).⁵⁵

Finally, the presence of tenosynovitis will be also recorded. The following 28 bilateral tendons will be assessed for Grayscale and Doppler tenosynovitis:

- Extensor compartments at the wrist (from 1-6),

- 2nd-5th finger flexor tendons,
- Tibialis posterior, flexor halluc longus, flexor digitorum common and peroneal tendons.

Evaluation and scoring will be performed according to the OMERACT definition and scoring system.⁵⁶

Note: All the specified 46 joints and 10 entheses should be evaluated at every visit indicated in [Appendix C](#). Only affected tendons will be assessed after Day 1 (Baseline). Standardized evaluation scans and examples of synovitis, enthesitis and tenosynovitis grading for each site examined will be available in an Atlas.

Details of US evaluation are presented in [Appendix J](#).

Dispense Study Drug, Dosing and Compliance

Adalimumab and MTX

Study medication(s), dosing instructions and a dosing diary will be dispensed to subjects beginning at Baseline (Day 1) and as specified in [Appendix C](#). Investigators will be provided with additional MTX product information from the manufacturer. The first dose of study drug(s) will be administered after all other Baseline (Day 1) procedures are completed.

MTX will be provided for either oral or subcutaneous (sc) administration as requested by the Investigator. ADA and sc MTX will be administered to subjects by study site medical staff, by him/herself or by a designee (friend, family member or health care professional) throughout the study.

Subjects or a designated family member or friend will be trained to administer study medication(s), if needed or considered appropriate, during the first visit or several times. This training must be documented in the subject's source document.

Subjects or a trained designated family member or friend or a health care professional will administer the injections of the study medication(s) in the subject's home or in the clinic during the weeks the subjects are not in the office for scheduled study visits.

For subjects that cannot/will not self-administer study medication(s) or do not have adequate support (friend, family member or healthcare professional) at home, administration will occur in the clinic.

On those days that a study visit takes place, study medication is to be administered after all clinical assessments including questionnaires, ultrasound evaluation (if applicable) and vital sign determination.

Adalimumab should be administered sc at approximately the same time of the day eow or ew, as per study protocol (with the exception of office visits). At all office visits, subjects should be observed after study drug administration until judged clinically stable by the study personnel. Study drug should be administered after all clinical assessments including questionnaires and vital sign determination. If an anaphylactic reaction or other serious allergic reaction occurs, administration of study medication should be discontinued immediately and appropriate therapy initiated. When dosing at home, subjects should be instructed to contact the site immediately with any signs or symptoms of a reaction. (See Section 6.1.7 for toxicity management).

MTX should be administered orally or sc at approximately the same time of the day ew. During the study subjects should continue with their regular MTX administration schedule prior to the study enrolment. If MTX is not routinely taken on the day of the study visit, the MTX will be dispensed to the subject and the subject will take the medication home and administer it at their regular schedule. There is no relation between the adalimumab and MTX administration schedule defined per this study protocol, but generally adalimumab and MTX are not recommended to be administered on the same day. See Section 5.5.1 Treatments Administered for additional information on MTX administration and dose escalation of MTX.

For subjects who deviate from the dosing schedule, every effort should be made to bring the subject back to the study Part 1 or 2 dosing schedule as soon as possible.

Subjects will maintain a dosing diary for all study drug administered outside of the study visit (i.e., at home) to capture dosing dates and times. The subject must be instructed to return study drug and diaries at each clinic visit for the purpose of compliance assessment and drug accountability as detailed in Section 5.5.7. At visits specified in Appendix C, the site personnel will review and retain a copy of the dosing diary, returned study drug kits, and empty study drug packaging to verify compliance. Additionally, any discernible departure from the protocol regarding study drug administration will be documented appropriately.

Randomization and Assignment of Subject Numbers

Subjects will be eligible for randomization if they continue to meet all of the selection criteria at Baseline and are willing to continue in the study.

Serum Adalimumab Concentrations

Samples will be obtained for serum adalimumab concentrations at the designated study visits as indicated in Appendix C and described in more detail under Section 5.3.2 only for subjects receiving adalimumab.

Anti-Adalimumab Antibodies (AAA)

Samples will be obtained for AAA at the designated study visits as indicated in Appendix C and described in more detail under Section 5.3.2 only for subjects receiving adalimumab.

Optional Samples for Exploratory Research and Validation Studies

Subjects will have the option to provide samples for exploratory research and validation studies. Subjects may still participate in the main study even if they decide not to participate in this optional exploratory research/validation studies. The procedure for

obtaining and documenting informed consent for exploratory research samples is discussed in Section [9.3](#).

Exploratory research can help to improve our understanding of how individuals respond to drugs and our ability to predict which subjects would benefit from receiving specific therapies. In addition, exploratory research may help to improve our understanding of how to diagnose and assess/monitor PsA by assessing associations between disease characteristics, outcomes data and biomarkers of interests.

Validation studies, including those related to the development of potential in-vitro diagnostic tests, may be carried out retrospectively in order to assess associations between events of interest (i.e., efficacy and/or safety events) and candidate biomarkers.

AbbVie (or people or companies working with AbbVie) will store the exploratory research/validation studies samples in a secure storage space with adequate measures to protect confidentiality. The samples will be retained while research on adalimumab (or drugs of this class) or this disease and related conditions continues, but for no longer than 20 years after study completion. Instructions for the preparation and shipment of the samples will be provided in a laboratory manual.

The following optional samples will be collected at the visits indicated in [Appendix C](#).

- A single whole blood sample for pharmacogenetic analysis will be collected at Day 1 or any subsequent visit (if not obtained on Day 1)
- Whole blood for epigenetic analysis
- Whole blood for transcriptomic
- Serum and Plasma Samples for systemic analyses, including but not limited to proteomic and metabolomic

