
[†] Current psoriasis is assigned a score of 2; all other features are assigned a score of 1.

The CASPAR criteria have specificity of 98.7% and sensitivity of 91.4%.

Vital Signs

Vital sign determinations of systolic and diastolic blood pressure in sitting position, pulse rate, respiratory rate, body weight, and body temperature will be obtained at each visit, as noted in [Appendix C](#). Blood pressure, pulse rate and respiratory rate should be performed before blood draws are performed. Height will be measured at the Screening Visit only and weight will be measured at the Screening visit and Week 32 or the premature discontinuation visit (with shoes off). All measurements will be recorded in metric units where applicable.

12-Lead Electrocardiogram (ECG)

A resting 12-lead ECG will be performed at the designated study visits as specified in [Appendix C](#). A qualified physician will interpret the clinical significance of any abnormal finding, sign, and date each ECG. Any clinically significant findings will be documented in the source documents and later transcribed on to the appropriate eCRF. Each signed original ECG will be monitored by the responsible site monitor and kept with the subject's source documents onsite.

For subjects with a normal ECG taken within 90 days of Screening, a repeat ECG at Screening will not be required, provided all protocol required documentation is available. If there are other findings that are clinically significant, the Investigator must contact the AbbVie TA MD before enrolling the subject.

Subjects can have a repeat ECG at any time during the study as warranted based on the opinion of the Investigator.

Chest X-Ray (CXR)

All subjects will undergo a standard CXR (posterior-anterior [PA] and lateral views) at the Screening visit to rule out the presence of TB or other clinically relevant findings. The CXR will not be required if the subject had a previous normal chest x-ray within 90 days of Screening, provided all protocol required documentation is available at the site (as outlined below) and provided nothing has changed in the subject's medical history to warrant a repeat test.

Subjects can have a repeat CXR at any time during the study as warranted based on the opinion of the Investigator.

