Optional Exploratory Research: Pharmacogenetic samples ^o		X										
Optional Exploratory Research: Epigenetic samples ^o		X	X	X			X				X	

Activity	Screening ^a	Day 1 Baseline	Week 2	Week 4	Week 8	Week 12	Week 16	Week 20	Week 24	Week 28	Week 32/PD	70 Day F/U Visit/Call
Optional Exploratory Research: Transcriptomic samples ^o		X	X	X			X				X	
Optional Exploratory Research: Samples for proteomic and targeted protein investigations (Plasma) ^p		X	X	X			X				X	
Optional Exploratory Research: Samples for proteomic and targeted protein investigations (Serum) ^p		X	X	X			X				X	

PD = Premature discontinuation; F/U = Follow-Up

- Perform within 30 days prior to study drug administration.
- Before study drug administration, all inclusion and exclusion criteria should be re-confirmed based on assessments completed during the Screening period.
- Update history.
- A symptom directed physical exam should be performed when necessary and if needed for physician assessments/questionnaires.
- Height will be measured at Screening only and weight will be measured at the Screening and Week 32/PD.
- For subjects with a normal ECG taken within 90 days of Screening, a repeat ECG at Screening will not be required.
- Chest x-ray not required at Screening if subject had a previous normal chest x-ray within 90 days of Screening.
- Subjects treated with corticosteroids (equivalent to Prednisone 5 mg or above – with ongoing treatment or treatment within 1 month to TB screening) must be screened with a QuantiFERON-TB Gold In-tube test or equivalent (central lab). Subjects NOT treated with corticosteroids can be screened with a PPD skin test (alternatively, also known as tuberculin skin test) locally or an Interferon-Gamma Release Assay (IGRA; QuantiFERON-TB Gold In-Tube test or T-SPOT TB test) centrally.
- Dipstick urinalysis will be completed by the central lab at all required visits. A microscopic analysis will be performed at Screening and in the event the dipstick results show protein, ketones or blood greater than negative or glucose greater than normal.

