5.0 Analysis Populations and Important Subgroups

5.1 Analysis Populations

Intent-to-Treat Population Part 1

The Intent-To-Treat Part 1 (ITT Part 1) population comprises all subjects who were randomized and received at least one dose of the study medication during the Part 1 period. The data collected up to Week 16 will be included and analyzed by the treatment

group assignment given at the time of randomization, even if the subject does not receive the correct treatment, is not compliant to the protocol procedures, or does not follow the protocol until completion.

Intent-to-Treat Population Long Term

The Intent-To-Treat Long Term (ITT LT) population comprises all subjects who entered Part 2 period and received at least one dose of Part 2 study medication. The data collected from randomization and up to Week 32 will be included and analyzed by the four treatment regimens as follows:

- ADA 40 mg eow + MTX 15 mg ew/ADA 40 mg eow
- ADA 40 mg eow + MTX 15 mg ew/ADA 40 mg ew + MTX 15 mg ew
- MTX 20 - 25 mg or highest tolerable dose ew
- MTX 20 - 25 mg or highest tolerable dose ew/ADA 40 mg eow + MTX 20 - 25 mg or highest tolerable dose ew

Per Protocol Population

In order to evaluate the impact of major protocol violations on the results of the trial, additional analysis of the primary effectiveness variable may be conducted on the per protocol population, which consists of all ITT Part 1 subjects who entered the randomized period of the study and did not meet any major protocol violation during the Part 1 of the study. The determination of major protocol violation will be finalized prior to the final database lock.

Safety Population Part 1

The Safety population Part 1 consists of all subjects who received at least one dose of the study medication during the Part 1 period. The data collected up to Week 16 will be included and analyzed by the two "As treated" treatment groups in Part 1. "As treated" is determined by the treatment a subject received during majority of the subject's drug exposure time in the analysis period, regardless of the treatment randomized.

Safety Population Part 2

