7.4 Analysis of Vital Signs and Weight

The vital sign variables are defined in Section 4.3.4.³ Observed values of vital sign variables which are measured longitudinally will be summarized at each visit by the two treatment groups in Part 1 and by the four treatment groups in Part 2, respectively. Summary statistics such as number of subjects, baseline mean, visit mean, standard deviation, minimum and maximum will be provided.

The criteria for potentially clinically significant vital sign findings are presented in Table 2. The number and percentage of subjects meeting the criteria for potentially clinically significant vital sign values will be summarized by the two treatment groups in Part 1 and by the four treatment groups in Part 2. Vital sign results satisfying the criteria for potentially clinically significant findings will be identified in a listing.

Table 2. Criteria for Potentially Clinically Significant Vital Sign Findings

Vital Sign	Category	Criteria for Potential Clinically Significant Vital Signs
Systolic blood pressure	Low	Value \leq 90 mmHg and decrease \geq 20 mmHg from Baseline
	High	Value \geq 160 mmHg and increase \geq 20 mmHg from Baseline
Diastolic blood pressure	Low	Value \leq 50 mmHg and decrease \geq 15 mmHg from Baseline
	High	Value \geq 105 mmHg and increase \geq 15 mmHg from Baseline
Pulse	Low	Value \leq 50 bpm and decrease \geq 15 bpm from Baseline
	High	Value \geq 120 bpm and increase \geq 15 bpm from Baseline
Weight	High	> 7% increase from baseline
	Low	> 7% decrease from baseline

The last evaluation prior to the first dose of study drug in Part 1 or Part 2 will be used as Baseline for Part 1 or Part 2, respectively.

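### Under the governing schedule, weight is taken only at Screening and Week 32 or discontinuation, so the SAP's separate Part 1 and Part 2 tables of >7% weight change cannot describe the periods they name

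*Protocol*

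**What the plan says.** **Protocol, schedule.** The Vital Signs paragraph of Section 5.3.1.1 contains two statements on weight. The first covers several vital signs together: "body weight, and body temperature will be obtained at each visit, as noted in" Appendix C. The second is specific: "weight will be measured at the Screening visit and Week 32 or the premature discontinuation visit". In Appendix C, the combined row for vital signs, weight and height is ticked at every visit from Screening to Week 32/PD (premature discontinuation), but its footnote e says that "weight will be measured at the Screening and Week 32/PD". Apart from the general sentence and the row's tick marks, nothing provides for a weight at Day 1 or Week 16.

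**SAP, analysis.** Table 2 in Section 7.4 includes weight, with the high criterion "> 7% increase from baseline" and a matching criterion for loss. Subjects meeting the criteria are counted for the two Part 1 groups and again for the four Part 2 groups, and are also listed. On baseline the section says: "The last evaluation prior to the first dose of study drug in Part 1 or Part 2 will be used as Baseline" for the respective part.

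**SAP, data windows.** Section 5.1 closes the Part 1 safety data at Week 16. It runs the Part 2 safety data from Week 16 to Week 32 and keeps data after the start of rescue medication out of the Part 2 analysis.

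**The concern.** A by-part table needs a weight near the start and near the end of each part. The specific schedule gives one weight before treatment and one at the end of participation, with nothing at the Week 16 boundary. Followed literally, the SAP rule would still produce percentages, but they would not mean what the table says. The Part 1 figure would rest on subjects who stopped early. The Part 2 figure would attribute to the regimen assigned at Week 16 any change that occurred on the randomized Part 1 treatment. Part 2 Arm 4 shows this most clearly: these subjects take methotrexate alone for 16 weeks before adalimumab is added, yet weight change from those weeks would be tabulated under adalimumab plus methotrexate. A reader comparing regimens on weight would be misled about both timing and treatment.

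**Working it through.** The plan states no figure that depends on this point, so there is nothing to reproduce. The check is to see which weights exist in each window and which value the baseline rule selects.

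**Inputs**
- Weight at Screening and at Week 32/PD (Protocol 5.3.1.1; Appendix C, footnote e).
- Screening within 30 days before first dose (Appendix C).
- Two parts of 16 weeks each (Protocol 5.1).
- 120 subjects per arm and 10% dropout (SAP 4.4).
- Safety windows and rescue rule (SAP 5.1); baseline rule and weight criterion (SAP 7.4).

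**Part 1**
1. The baseline is the last weight before the first dose, which is the Screening weight.
2. The only scheduled later weight that can fall by Week 16 is at a PD visit.
3. At 10% dropout, with every dropout in Part 1 and attending a PD visit: 0.10 × 120 = 12 per arm, or 24 of 240. The other 240 − 24 = 216 have no second weight in Part 1.
4. If dropout were 5% to 15% (an assumption), the count would be 6 to 18 per arm, or 12 to 36 in total.
5. SAP 7.4 gives no denominator. If all 120 per arm are used, at least 108 of 120 (90%) count as not meeting the criterion without having been re-weighed. If only those weighed are used, the table describes discontinuers.

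**Part 2**
1. With no Week 16 weight, the last weight before the first Part 2 dose is again the Screening weight.
2. Interval for an unrescued Week 32 completer: 32 × 7 = 224 days on treatment, plus 0 to 30 days of screening, gives 224 to 254 days.
3. Length of Part 2: 16 × 7 = 112 days.
4. Share of the interval that is Part 2: 112/254 = 44% to 112/224 = 50%. The remaining 112 to 142 days are Part 1 treatment and screening.
5. For a subject who leaves during Part 2, the interval runs from Screening to the PD visit and is shorter.
6. For a rescued subject, the Week 32 or PD weight comes after rescue started and is excluded. No earlier Part 2 weight is scheduled, so that subject normally contributes nothing to the Part 2 rows.

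**The case against.** **Weight may be taken at every visit.** The general sentence in Protocol 5.3.1.1 and the tick marks in Appendix C both point that way. If sites followed them, Day 1 and Week 16 weights exist and both problems disappear. This stands as a condition on the finding. The restrictive reading is still the better one, because the general sentence defers to Appendix C and the footnote there restricts weight. The SAP does not settle the matter: Section 7.4 refers to Section 4.3.4 for the vital sign variables, and that section does not list them. If sites read the text differently, weights would be available unevenly, which is a further reason to reconcile it.

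**The consequences are small.** This is correct. The table is descriptive, no test is planned for it, SAP 7.1 does not impute missing safety data, and subjects meeting the criteria are listed individually. A reader might infer that the trial's safety or efficacy conclusions are compromised. The documents do not support that: the primary analysis does not use weight, and the Screening weight still supplies the baseline weight covariate for the ultrasound model (SAP 6.4).

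**The sizes can be overstated.** This is also correct. Twelve per arm is an upper bound at the planning dropout rate, not an expected count, because Protocol 5.4.1 provides for subjects lost to follow-up, who may have no PD visit. Likewise, a reader might infer that every Part 2 weight change covers the whole study. That holds only for unrescued Week 32 completers.

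**Conclusion.** The by-part weight rows in SAP 7.4 do not fit the governing weight schedule. Part 1 can include only subjects with a PD visit by Week 16, at most about 12 of 120 per arm at 10% dropout. For unrescued completers, the Part 2 rows report a change over 224 to 254 days as if it belonged to a 112-day period and its regimen.

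This rests on two assumptions: that the restrictive sentence and footnote e govern, and that sites did not record weights beyond the schedule. The documents cannot show what sites actually did, so a reader should not conclude that Week 16 weights are certainly absent. What is established is that the protocol text conflicts with itself and that, under its more specific reading, the SAP rule gives mislabelled results. The matter is minor but worth correcting, since it affects one descriptive table and its listing. The SAP already makes the corresponding check for ECGs: Section 7.5 plans no analysis because there were no post-baseline recordings.

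**What to change.** 1. **Protocol:** make the two sentences in the Vital Signs paragraph of Section 5.3.1.1 agree with each other and with the Appendix C row and footnote.
2. **SAP 7.4:** remove weight from the by-part rows. Report a single change in weight from Screening to Week 32/PD, labelled with that interval, using the number of subjects weighed at both points as the denominator.
3. **Grouping:** show subjects who entered Part 2 by the four treatment sequences in SAP 5.1. Show those who left in Part 1 by randomized arm, because they have no sequence and a table by sequence alone would omit them.
4. **Rescue:** show weights taken after rescue started separately, in line with the SAP 5.1 rule for Part 2 safety data.

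Items 2 to 4 cost only SAP wording and one re-specified table. Adding a Week 16 weight is an alternative that would give Part 1 an end value and Part 2 a proper baseline. It needs a protocol amendment and helps only subjects who have not yet passed that visit. The SAP describes randomization in the past tense, which suggests, without proving, that many already had.
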